***The use of an embolic protection device during the TAVI procedure is not permitted.***

**Pre-Procedure**

- Pre-medication recommendations:
  - If the subject is currently on warfarin therapy, or local equivalent, prior to the procedure:
    - Discontinue warfarin therapy 3 days prior to the procedure
    - Confirm that the INR < 1.8 prior to the procedure
    - Administer antiplatelet therapy:
      - Aspirin (75- 325 mg) daily **or**
      - Clopidogrel (75 mg) daily (or ticlopidine if clopidogrel is contraindicated) for 3 days prior to the procedure
  - If the subject is currently **not** on warfarin therapy prior to the procedure:
    - Aspirin (75-325 mg) on the day of the procedure **and**
    - Clopidogrel (300 mg)
  - Consider adjunctive proton pump inhibitors, H2 antagonists or antacids
- Routine Laboratory Tests:
  - Complete Blood Count
    - White Blood Count
    - Hematocrit
    - Hemoglobin
    - Platelet Count
  - Creatinine and Creatinine Clearance
    - If the GFR < 60 cc/min, consider:
      - Fluid hydration on the day prior to the procedure
      - Discontinuation of NSAIDs and ACE inhibitors
  - Cardiac Enzymes (CK/CK-MB)
  - International Normalized Ratio (INR), if applicable
  - Activated Partial Thromboplastin Time (aPTT)
  - B-type Natriuretic Peptide (BNP) or NT-proBNP
  - Liver Panel:
    - ALT
    - AST
    - Albumin
  - Sodium
  - Potassium
- 12-lead Electrocardiogram (ECG)

**TAVI Procedure**

- *Medications*

One hour prior to the procedure, prophylactic antibiotic therapy of the Investigator's choice should be initiated:

  - Cefuroxime 750mg intravenous (IV) 1 hour pre-procedure, then 6 hours and 12 hours post-procedure
  - If allergic to Penicillin, prescribe Vancomycin 1g IV
  - Consider holding anti-hypertensives
- *Anesthesia and Procedural Set Up*
  - Establish a central venous line
  - Administer general anesthesia or conscious sedation per hospital protocol
  - Prior to beginning the investigational TAVI device system implant, place a temporary 4-5 Fr. balloon-tip pacing wire in a stable location within the right ventricular (a screw-tip wire may be used for more secure placement for subjects at high-risk for dislodgement, if necessary)
  - Whenever possible, use the upper torso venous system (eg. jugular, subclavian) for temporary pacing wire access
  - Use fluoroscopy to guide wire placement and stability
  - Confirm sensing and capture
  - Program the backup pacing rate to minimize ventricular pacing (eg. 30-40 bpm). If heart block develops, adjust the rate accordingly
  - Record ECG and angiogram during the procedure
- *Vascular Access*

- The primary access artery will be used to introduce the CoreValve device and the balloon catheter; the secondary access artery will be used to introduce the reference pigtail
- Insert a 6Fr introducer sheath into the secondary access artery
- Insert 18Fr introducer sheath into the primary access artery using hospital protocol (either percutaneously or surgical cut down)
- Administer anticoagulant therapy according to hospital protocol. If heparin is administered as an anticoagulant, check activated clotting time (ACT) at five minutes and monitor every 30-60 minutes after initial bolus of heparin
- Maintain ACT  $\geq$  250 seconds
- Anticoagulant may be administered at any time prior to this point, but avoid delaying beyond this point
- *Crossing the native valve*
  - Advance the graduated pigtail catheter to the ascending aorta and position the distal tip in the noncoronary cusp of the native aortic valve
  - Identify the ideal annular viewing plane using contrast injections at various angiographic angles, preferably in the left anterior oblique (LAO) projection.
    - An aortogram with the three aortic cusps aligned in one (1) plane should be obtained in order to proceed with the procedure and guarantee an optimal working view for eventual implantation
  - Insert an angiographic catheter over a standard, J-tip guidewire into the primary access sheath and advance to the ascending aorta
  - Exchange the J-tip guidewire for a 0.035-in (0.889-mm) straight-tip guidewire. Advance the straight-tip guidewire across the native aortic valve into the left ventricle
  - After crossing the native aortic valve with the guidewire, advance the angiographic catheter into the left ventricle
  - Exchange the straight-tip guidewires for an exchange-length J-tip guidewire
  - Exchange the angiographic catheter for a 6Fr pigtail catheter
  - Remove the guidewire and connect the catheter to the transducer. Using both catheters, record the aortic pressure gradient
  - Using a right anterior oblique (RAO) projection, advance previously pigtail-shaped, 0.035-in (0.889-mm) high-support guidewire through the pigtail catheter and position in the apex of the left ventricle
  - Remove the pigtail catheter while maintaining guidewire position in the left ventricle
- *Rapid Pacing and Pre-dilatation of the Implant site*
  - Insert the valvuloplasty balloon through the 18Fr introducer sheath and advance it to the ascending aorta
  - Perform a rapid pacing test. A successful test is defined as 1-to-1 pacing capture with an immediate drop in pressure and elimination of the systolic-diastolic waveform
  - Reposition the angiographic equipment to the ideal viewing plane as previously described. Position the valvuloplasty balloon across the native valve, while maintaining strict fluoroscopic surveillance of the distal tip of the guidewire in the left ventricle (LV)
  - Perform BAV per hospital protocol and remove the valvuloplasty balloon while maintaining guidewire position across the native aortic valve
  - Balloon sizing directed to 1:1 sizing of the minimal annular diameter by computerized tomographic angiography (CTA) or echocardiogram with maximum 25 mm balloon
  - Perform full balloon expansion

- *Medtronic CoreValve™ Implantation*
  - Insert the device over the 0.035-in (0.889-mm) guidewire and advance it, while maintaining strict fluoroscopic surveillance of the guidewire in the LV
  - When crossing the aortic arch, control the guidewire preventing it from moving forward
  - Advance the device through the native valve. Perform an angiogram to confirm that the graduated pigtail catheter is in position within the noncoronary cusp of the aortic root, preferably in the shallow LAO projection
  - Use Fluoroscopy to identify the appropriate landmarks
  - Place the bioprosthesis within the aortic annulus. Optimal placement of the bioprosthesis is 4 mm - 6 mm below the annulus. The annulus is defined as the angiographic floor of the aortic root
  - After attaining optimal catheter position, slowly turn the micro knob and begin to deploy the bioprosthesis. As the inflow aspect of the bioprosthesis starts to flare outward, monitor bioprosthesis position under fluoroscopy
  - Caution: During implantation, if resistance to deployment is encountered (for example, the micro knob starts clicking or is tight or stuck), apply mild upward pressure to the macro slider while turning the micro knob. If the bioprosthesis still does not deploy, remove it from the patient and use another system
  - Perform an angiogram. Once annular contact is made, the bioprosthesis should not be advanced into a lower position
  - Continue deploying rapidly to the 2/3 deployment point; stop turning the micro knob
  - Perform an angiogram to assess the location of the bioprosthesis.
  - If the bioprosthesis is positioned low, carefully pull the DCS to reposition the bioprosthesis
  - Evaluate the valve position and valve function using hemodynamic, aortography, and possible echocardiography
  - When satisfactory position is achieved, continue to turn the micro knob until both frame loops disengage
  - Use orthogonal views under fluoroscopy to confirm that the frame loops have detached from the catheter tabs. If a frame loop is still attached to a catheter tab, under fluoroscopy, advance the catheter slightly and, if necessary, gently rotate the handle clockwise (<math><180^\circ</math>) and counterclockwise (<math><180^\circ</math>) to disengage the loop from the catheter tab
  - Withdraw the DCS carefully to the aorta avoiding contact with the inflow portion of the frame while maintaining guidewire position
- *Medtronic CoreValve™ Post Deployment*
  - Close the DCS capsule and remove the DCS through the 18Fr introducer sheath
  - Advance a 6Fr pigtail catheter over the guidewire into the left ventricle
  - Remove the guidewire and connect the pigtail catheter to the transducer
  - Using both pigtail catheters, record aortic pressure gradient
  - Withdraw 6Fr pigtail
  - Perform post-implant aortogram with the reference pigtail to assure coronary patency and assess aortic regurgitations. Aortogram Acquisition Guidelines are located in **Appendix R.6**
  - Remove the 18Fr introducer sheath and complete the puncture site closure per hospital protocol
  - Perform contrast angiography of the primary vessels to verify the absence of any vascular complications with the reference pigtail
  - Remove the reference pigtail catheter over a standard guidewire
  - Remove the 6Fr introducer and close the access site per hospital protocol

Ballooning as needed during the implant procedure is standard practice and should not be considered a reintervention.

### **Immediate Post-Procedure**

The procedure is considered complete after final angiography has been performed, and the introducer/InLine sheath has been removed from the subject. Thereafter, if an introducer/InLine sheath is re-introduced, this is considered a repeat intervention, which must be documented on the reintervention Electronic Case Report Form (eCRF).

- Coronary Arteriogram
- Following the current recommendation all patients with prosthetic heart valves need endocarditis prophylaxis
- All patients should receive Deep Vein Thrombosis (DVT) prophylaxis with Heparin/Low Weight Molecular Heparin (LMWH) starting approximately 6 hours after TAVI if bleeding permits
- Anticoagulants should be discontinued per hospital standard
- Activated clotting time (ACT) should be monitored per hospital standards but recommendation is >250 seconds
- Cardiac Enzymes: CK within 8-12 hours post procedure and at any time when a clinical ischemic event is suspected.
  - CK-MB is required if CK is elevated  $\geq 2X$  the laboratory upper limit of normal.
  - If a clinical event is confirmed, a total of 3 draws of cardiac enzymes within the first 24 hours (drawn approximately every 8 hours) following the clinical event should be obtained
- 12-lead Electrocardiogram (ECG) to be performed within 48 hours of procedure
- Abbreviated Neurological Assessment
  - National Institute of Health Stroke Scale (NIHSS) to be completed with 24 hours of procedure
- Transthoracic Echocardiogram (TTE)
  - Comprehensive transthoracic 2D echocardiogram (TTE) should be performed within 24-48 hours post-procedure or prior to discharge to assess device success. Echocardiograms will be performed according to Echocardiography Procedures found in **Appendix R.7**
- It is recommended that subjects are treated for a minimum of three months with dual anti-platelet medication
  - If the patient is on warfarin therapy post-procedure it is recommended that subjects are prescribed either daily:
    - Aspirin (75 to 325 mg) **or**
    - Clopidogrel (75 mg) (or ticlopidine, if clopidogrel is contraindicated) for at least three months following the procedure
  - If the patient will **not** be on warfarin therapy post-procedure it is recommended that subjects are prescribed daily:
    - Aspirin (75to 325 mg) **and**
    - Clopidogrel (75 mg) (or ticlopidine, if clopidogrel is contraindicated) for at least three months following the procedure
- Concomitant medications
- Adverse events review
  - Document all adverse events, including all unanticipated adverse device effects (UADE) or unanticipated serious adverse device effects (USADE), technical observations, reinterventions or repeat admissions to the catheterization suite and deaths
  - Any patient with evidence of a new neurological event should have a neurology consult and subsequently an imaging trial if deemed necessary by the neurologist or stroke specialist
  - Any patient exposed to substantial radiation dose levels, as outlined in **Appendix R.23**, should be assessed for skin reactions

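### The TAVI post-procedure list recommends an ACT above 250 seconds directly after telling sites to stop anticoagulants, when both arterial access sites are already closed

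*Combined protocol and SAP*

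**What the plan says.** All of the relevant text is in section C.4.7.1 (TAVI).

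- **Vascular Access.** The 6Fr and 18Fr sheaths are inserted. The instruction on drugs is "Administer anticoagulant therapy according to hospital protocol". If heparin is used, ACT is checked at five minutes and then every 30-60 minutes, and it is to be kept at or above 250 seconds.
- **Post Deployment.** The closing steps include "Remove the 18Fr introducer sheath and complete the puncture site closure per hospital protocol" and, last, "Remove the 6Fr introducer and close the access site per hospital protocol".
- **Immediate Post-Procedure.** The opening sentence is "The procedure is considered complete after final angiography has been performed, and the introducer/InLine sheath has been removed from the subject". The next begins "Thereafter, if an introducer/InLine sheath is re-introduced, this is considered a repeat intervention", to be documented on its own form. In the list that follows, heparin or low-molecular-weight heparin for DVT prophylaxis is given "starting approximately 6 hours after TAVI if bleeding permits". The next bullet is "Anticoagulants should be discontinued per hospital standard", and the one after that is "Activated clotting time (ACT) should be monitored per hospital standards but recommendation is >250 seconds".

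**The concern.** A target of 250 seconds makes sense while catheters and sheaths are in the arteries. The Immediate Post-Procedure list applies after they have been removed. A site that follows the list literally is told to stop anticoagulants and, in the next line, is given a recommended clotting time that would normally need them, over an 18Fr puncture that has just been closed. Sites should not have to guess which line governs.

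What is at stake is the clarity of a clinical instruction. The sample size, the type I error rate and the endpoint definitions do not depend on it.

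**Working it through.** No formula applies, and the plan has no figure to reproduce. The check is to read the TAVI steps in order and compare them.

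| Point in C.4.7.1 | State of the arterial access | What is said about anticoagulation or ACT |
|---|---|---|
| Vascular Access | 6Fr and 18Fr sheaths inserted | Anticoagulant per hospital protocol; ACT at least 250 seconds |
| Post Deployment, closing steps | 18Fr site closed, then 6Fr site closed | Nothing |
| Immediate Post-Procedure, prophylaxis bullet | Both sites closed | Heparin/LMWH from about 6 hours, if bleeding permits |
| Immediate Post-Procedure, next bullet | Both sites closed | Discontinue anticoagulants per hospital standard |
| Immediate Post-Procedure, bullet after that | Both sites closed | Monitor ACT per hospital standards, but above 250 seconds recommended |

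**Timing.** From removal of the 18Fr sheath onward, Post Deployment has four steps: remove that sheath and close; angiography of the primary vessels; remove the reference pigtail; remove the 6Fr introducer and close. These close 2 of the 2 arterial sites opened at Vascular Access. The completion sentence then places the list after sheath removal. The central venous line and temporary pacing wire are separate. Pacing continues for at least 48 hours, but neither the set-up steps nor the pacing guidelines tie an ACT level to those lines.

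**Level.** An ACT level is stated twice for TAVI: at least 250 seconds during the procedure and above 250 seconds afterwards. These are essentially the same level. The list supplies no anticoagulant to sustain it before the 6-hour prophylaxis.

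**Could the bullet be meant for something narrower?** The in-procedure period is already covered at Vascular Access. A re-introduced sheath is classed as a repeat intervention, and the ACT bullet is not limited to that case.

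**Comparison with SAVR.** In C.4.7.2, ACT is left to local practice for bypass. Neither the SAVR post-procedure list nor the Post-Procedural Medication list gives an ACT level.

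**After the edit.** The level is stated 2 - 1 = 1 time, at Vascular Access. The remaining bullet, monitoring per hospital standards, agrees with the bullet before it.

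**The case against.** The strongest reply is that the conflict is soft. Both bullets refer to hospital standards and neither gives a time. If a hospital stops anticoagulants some time after sheath removal, both could apply for a while. Implant teams must have at least 30 cumulative TAVI procedures, so few would chase an ACT of 250 seconds over a closed puncture. The documents give no normal ACT range and no closure threshold. The Instructions for Use are supplied separately, and only part 3 of 4 of the document is available, so governing guidance elsewhere cannot be excluded.

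Much of this stands, and it is why the point is minor. It does not remove the inconsistency. The ACT bullet sets its recommendation against hospital standards with the word but, so it does not simply defer to them. Nothing in the available text confines it to the time before closure.

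A reader might infer three stronger things that the documents do not support:

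- **That the phrase was carried over from the procedural steps**, since the same list opens with a coronary arteriogram, which Table 3 puts in the Procedure column. That column also holds plainly post-procedure items: the ECG within 48 hours, the NIHSS within 24 hours and the TTE at least 24 hours after the procedure. Being in that column therefore does not show that an item is misplaced. The reason for the phrase is unknown.
- **That the 6-hour bullet contradicts the ACT line.** It schedules DVT prophylaxis and is silent on procedural anticoagulation before then. Its condition about bleeding pulls the other way from a high ACT, which is tension only.
- **That the TAVI arm's bleeding or vascular results would be distorted**, because the line exists only for TAVI and C.6.10.1 tests both outcomes (items 14 and 15). The documents give no figure from which such an effect could be computed.

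**Conclusion.** The point holds as a minor inconsistency in safety text. Two adjacent bullets, in a list that begins after both arterial sites are closed, point in opposite directions. Confidence is high on the juxtaposition and does not extend to its cause.

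The line is advisory, so actual harm is unlikely. No effect on any endpoint, on power or on a labeling claim is asserted.

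The conclusion rests on two assumptions. The first is that an ACT above 250 seconds would ordinarily require anticoagulant. This is general clinical knowledge; the protocol gives no reference range, although it does tie ACT checks to the heparin bolus. The second is that no other part of the document, and no Instructions for Use, limits the bullet to an earlier stage. The documents do not say how many TAVI procedures remained to be done; if few, the benefit of the edit is smaller.

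**What to change.** In the TAVI Immediate Post-Procedure list, delete the closing clause that gives the 250-second level. The bullet then says only that ACT is monitored according to hospital standards. Leave the Vascular Access target of at least 250 seconds as it is. Add no new end point tied to sheath removal, because anticoagulation and closure are already left to hospital protocol.

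Record the edit in the next amendment of the clinical investigation plan and notify sites by letter. A letter alone is not enough: section N requires amendments to be agreed between sponsor and investigators and entered with a justification in Table 8. Significant amendments also go to the regulatory authorities and the IRB/MEC.

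The cost is one clause, one Table 8 entry with the agreement behind it, and one letter. No patient, assessment, analysis or clinical instruction is added.

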### **Post-Procedure Pacing Guidelines**

- All patients should stay on telemetry until discharge
- Maintain temporary pacing until at least 48 hours post-implant in Cardiovascular Intensive Care Unit (CV-ICU) or local equivalent
- After 48 hours, obtain ECG and assess patient rhythm and conduction
- Based on assessment, and with the consult of an electrophysiologist as needed, take one of the following actions:
  - Discontinue temporary pacing
  - Continue temporary pacing for another 24 hours (longer if needed) to make further assessments
  - Place a permanent pacemaker according to ACC/AHA/HRS Guidelines for Device-Based Therapy of Cardiac Rhythm Abnormalities (Class I or IIb for Acquired Atrioventricular Block in Adults or Permanent Pacing in Chronic Bifascicular Block) as outlined in **Appendix R.13**
  - Prior to the permanent pacemaker implantation, document the reason for the placement of the permanent pacemaker via a 12-lead ECG
  - For complete heart block, review patient medications
  - Consider withholding some medications to assess for patient's intrinsic rate and conduction
  - If heart block persists off medications, a permanent pacemaker should be considered
  - If a permanent pacemaker is required, a dual chamber system is recommended to optimize patient hemodynamics
  - For additional information refer to the Pacing Guidelines in **Appendix R.13**

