### R.13 Pacing Guidelines

Recommendations for pacing pre-, peri- and post-operatively are provided below (see also respective investigational device Instructions For Use). These are recommendations and final decisions should be made via clinical presentation and physician discretion. Programmed settings for temporary and permanent pacing are per subject condition and physician discretion.

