#### Post-operative Recommendations

- All subjects should stay on telemetry until discharge
- Maintain temporary pacing until at least 48 hours post-implant
  - Ensure a clean, sterile environment is maintained
- After 48 hours, obtain ECG and assess subject rhythm and conduction
  - Based on assessment, and with the consult of an electrophysiologist as needed, take one of the following actions:
    - Discontinue temporary pacing
    - Continue temporary pacing for another 24 hours (longer if needed) to make further assessments

- Place a permanent pacemaker according to ACC/AHA/HRS Guidelines for Device-Based Therapy of Cardiac Rhythm Abnormalities (Class I or IIa for Acquired Atrioventricular Block in Adults or Permanent Pacing in Chronic Bifascicular Block)
  - Prior to the permanent pacemaker implantation, document the reason for the placement of the permanent pacemaker via a 12-lead ECG.
- For complete heart block, review subject medications. Consider withholding some medications to assess for subject's intrinsic rate and conduction. If heart block persists off medications, a permanent pacemaker should be considered.
- If a permanent pacemaker is required, a dual chamber system is recommended to optimize subject hemodynamics.
  - **Recommended AV conduction assessment:**
    - Conduct an atrial threshold test with a long AV delay (350ms) in DDD mode.
    - If the subject's ventricular rhythm doesn't come through within the 350 ms, the subject would be considered dependent on ventricular pacing.

---

 ACC/AHA/HRS 2008 Guidelines for Device-Based Therapy of Cardiac Rhythm Abnormalities: J Am Coll Cardiol 2008; 51:2085–105; Circulation 2008;117:2820–40

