### Recommendations for Acquired Atrioventricular Block in Adults

Class I Permanent pacemaker implantation is indicated for:

- Third-degree and advanced second-degree atrioventricular (AV) block at any anatomic level associated with bradycardia with symptoms (including heart failure) or ventricular arrhythmias presumed to be due to AV block. (LOE: C)
- Third-degree and advanced second-degree AV block at any anatomic level associated with arrhythmias and other medical conditions that require drug therapy that results in symptomatic bradycardia. (LOE: C)
- Third-degree and advanced second-degree AV block at any anatomic level in awake, symptom-free patients in sinus rhythm, with documented periods of asystole greater than or equal to 3.0 seconds or any escape rate less than 40 bpm, or with an escape rhythm that is below the AV node. (LOE: C)
- Third-degree and advanced second-degree AV block at any anatomic level in awake, symptom-free patients with atrial fibrillation and bradycardia with 1 or more pauses of at least 5 seconds or longer. (LOE: C)
- Third-degree and advanced second-degree AV block at any anatomic level after catheter ablation of the AV junction. (LOE: C)
- Third-degree and advanced second-degree AV block at any anatomic level associated with postoperative AV block that is not expected to resolve after cardiac surgery. (LOE: C)
- Third-degree and advanced second-degree AV block at any anatomic level associated with neuromuscular diseases with AV block, such as myotonic muscular dystrophy, Kearns-Sayre syndrome, Erb dystrophy (limb-girdle muscular dystrophy), and peroneal muscular atrophy, with or without symptoms. (LOE: B)
- Second-degree AV block with associated symptomatic bradycardia regardless of type or site of block. (LOE: B)
- Asymptomatic persistent third-degree AV block at any anatomic site with average awake ventricular rates of 40 bpm or faster if cardiomegaly or left ventricular (LV) dysfunction is present or if the site of block is below the AV node. (LOE: B)
- Second- or third-degree AV block during exercise in the absence of myocardial ischemia. (LOE: C)

Class IIa Permanent pacemaker implantation is reasonable for:

- Persistent third-degree AV block with an escape rate greater than 40 bpm in asymptomatic adult patients without cardiomegaly. (LOE: C)
- Asymptomatic second-degree AV block at intra or infra-His levels found at electrophysiological study. (LOE: B)

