- First- or second-degree AV block with symptoms similar to those of pacemaker syndrome or hemodynamic compromise. (LOE: B)
- Asymptomatic type II second-degree AV block with a narrow QRS. When type II second-degree AV block occurs with a wide QRS, including isolated right bundle-branch block, pacing becomes a Class I recommendation (see Section 2.1.3, "Chronic Bifascicular Block," in the full-text guidelines). (LOE: B)

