### Recommendations for Permanent Pacing in Chronic Bifascicular Block

Class I Permanent pacemaker implantation is indicated for:

1. Advanced second-degree AV block or intermittent third-degree AV block. (LOE: B)
2. Type II second-degree AV block. (LOE: B)
3. Alternating bundle-branch block. (LOE: C)

Class IIa Permanent pacemaker implantation is reasonable for:

- Syncope not demonstrated to be due to AV block when other likely causes have been excluded, specifically ventricular tachycardia (VT). (LOE: B)
- Incidental finding at electrophysiological study of a markedly prolonged HV interval (greater than or equal to 100 milliseconds) in asymptomatic patients. (LOE: B)
- Incidental finding at electrophysiological study of pacing-induced infra-His block that is not physiological. (LOE: B)

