The incidence of conduction disturbance requiring permanent pacemaker implantation will be provided at 30 days, 6 months, 12 months, 18 months, 24 months, and annually thereafter up to 5 years, separately for new onset and pre-existing conduction disturbance. The statistical method will be the Bayesian version of a comparison of proportions (with predictions).

8. Change in NYHA class from baseline at 30 days, 6 months, 12 months, 18 months, 24 months, and annually thereafter up to 5 years.

For each subject with paired data, the number of classes changed from baseline (-3, -2, -1, 0, 1, 2, or 3) will be calculated at 30 days, 6 months, 12 months, 18 months, 24 months, and annually thereafter up to 5 years. The endpoint will be evaluated between groups using a Bayesian version of a t-test.

9. Change in distance walked during 6-minute walk test (6MWT) from baseline to 30 days, baseline to 12 months, and baseline to 24 months.

All subjects who are able to perform the six-minute walk evaluation at the time of the follow-up visit will be included in the analysis.

The endpoint will be evaluated using a Bayesian version of a t-test.

10. Ratio of days alive out of hospital versus total days alive assessed at 12 months and 24 months follow-up.

The proportion of post procedure days alive out of hospital against total days alive will be compared between groups at 12 and 24 months. The numerator will be the number of days alive out of hospital, and the denominator will be the number of post procedure days alive as of the last follow-up date. All hospitalizations will be included in this analysis, including hospitalization for device implant.

In addition, days alive out of hospital will be compared between groups at 12 months and 24 months.

The endpoint will be evaluated using a Bayesian version of a t-test.

11. Quality of Life (QoL) change from baseline at 30 days, 3 months, 6 months, 12 months, 18 months, 24 months, and annually thereafter up to 5 years.

The Kansas City Cardiomyopathy Questionnaire (KCCQ), SF-36, and EuroQoL (EQ-5D) will be assessed at baseline, 30 days, 6 months, 12 months, 18 months, 24 months, and annually thereafter up to 5 years. SF-36 and EQ-5D will also be assessed at 3 months. All subjects completing the questionnaires will be evaluated and the reasons for missing data will be provided.

The endpoint will be evaluated using a Bayesian version of a t-test.

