## **CONDUCTION DISTURBANCE REQUIRING PERMANENT PACEMAKER IMPLANTATION**

ACC/AHA 2006 Guidelines for the Management of Patients with Valvular Heart Disease (published in the August 1, 2006, issues of Journal of the American College of Cardiology and Circulation)

Any disturbance in the cardiac electrical conduction system that meets the American College of Cardiology (ACC)/American Heart Association (AHA)/ Heart Rhythm Society (HRS) Class I or IIa Guidelines for Device-Based Therapy of Cardiac Rhythm Abnormalities for Acquired Atrioventricular Block in Adults or Permanent Pacing in Chronic Bifascicular Block.

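### The TAVI and SAVR pacing sections give the pacemaker criterion as Class I or IIb, whereas the appendix they cite and the definition of secondary endpoint 7 give Class I or IIa (minor)

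*Combined protocol and SAP*

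**What the plan says.** The Post-Procedure Pacing Guidelines appear twice in the protocol body, in C.4.7.1 for TAVI and in C.4.7.2 for SAVR. In both, one of the actions open to the site after the 48-hour rhythm assessment is to place a permanent pacemaker under the ACC/AHA/HRS device guideline. Both give the qualifying indications as "Class I or IIb for Acquired Atrioventricular Block in Adults or Permanent Pacing in Chronic Bifascicular Block" and refer the reader to Appendix R.13.

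Appendix R.13, under Post-operative Recommendations, gives the same instruction with a different class: "Class I or IIa for Acquired Atrioventricular Block in Adults or Permanent Pacing in Chronic Bifascicular Block". It then sets out the indications for each of the two conditions, under Class I and Class IIa headings only.

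Section O.2 defines conduction disturbance requiring permanent pacemaker implantation as one that meets the "Class I or IIa Guidelines for Device-Based Therapy of Cardiac Rhythm Abnormalities", for the same two conditions. Secondary endpoint 7 in C.6.8.1 uses that term: "The incidence of conduction disturbance requiring permanent pacemaker implantation will be provided at 30 days" and at later visits up to 5 years, compared between the arms.

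**The concern.** The criterion for placing a permanent pacemaker is stated in the procedure section of each arm, in the appendix both sections cite, and in the definition behind a comparative secondary endpoint. These should name the same guideline classes, and they do not.

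Read literally, the body text causes two problems. A site could treat a Class IIa indication as outside the instruction, although the appendix lists it as a reason to implant. A site could also implant for a Class IIb indication, for which the appendix gives no criterion and which the O.2 definition of the endpoint 7 term does not cover. Such an implant would follow the procedure section yet fall outside that definition.

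At stake are clear guidance on a common post-procedure decision and agreement between what sites are told to do and what endpoint 7 is defined to count. The primary endpoint of all-cause mortality or disabling stroke is not involved.

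**Working it through.** The plan states no figure to reproduce. The check compares the texts and counts the listed criteria.

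**Classes named in each place**

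| Place | Class named |
|---|---|
| C.4.7.1, Post-Procedure Pacing Guidelines (TAVI) | I or IIb, referring to R.13 |
| C.4.7.2, Post-Procedure Pacing Guidelines (SAVR) | I or IIb, referring to R.13 |
| Appendix R.13, Post-operative Recommendations | I or IIa |
| Appendix R.13, acquired AV block list | I and IIa headings only |
| Appendix R.13, chronic bifascicular block list | I and IIa headings only |
| O.2, conduction disturbance requiring permanent pacemaker implantation | I or IIa |

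The body sections and the R.13 recommendation use the same phrase, with only the class label changed. All six places are current operative text, not an amendment log, and no redaction or broken table is involved. Because R.13 and O.2 agree with each other, the error lies in the two body sections.

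**Criteria listed in Appendix R.13**

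| Condition | Class I | Class IIa | Class IIb |
|---|---|---|---|
| Acquired AV block in adults | 10 | 4 | 0 |
| Chronic bifascicular block | 3 | 3 | 0 |
| Total | 13 | 7 | 0 |

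- All listed criteria: 13 + 7 = 20.
- Kept under a literal reading of Class I or IIb: 13 + 0 = 13.
- Dropped: 7, which is 7/20 = 35% of the listed criteria.
- Added: a class with no listed criterion.

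**What is dropped.** The acquired AV block Class IIa list includes "Persistent third-degree AV block with an escape rate greater than 40 bpm in asymptomatic adult patients without cardiomegaly" and "First- or second-degree AV block with symptoms similar to those of pacemaker syndrome or hemodynamic compromise". The bifascicular block list also has its own heading, "Class IIa Permanent pacemaker implantation is reasonable for", with three entries. Separate bullets in both body sections deal with complete heart block and say a pacemaker should be considered if the block persists off medication. They cover the first of these criteria at least in part. They do not clearly cover symptomatic first- or second-degree block.

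**What cannot be computed.** The documents give no split of pacemaker implants by guideline class, so the 35% cannot be turned into a change in the endpoint 7 rate.

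**The case against.** The mismatch itself is not in dispute. The case on the other side is that it has little consequence.

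- **The appendix contains the slip.** The body text ties the class to what R.13 outlines, and R.13 outlines no Class IIb criterion. Each section points to R.13 twice, so a site that looks up the criteria finds only Classes I and IIa. This stands as a limit on the effect. It does not make the label right; it shows which text is wrong.
- **This is guidance, not a binding rule.** R.13 opens by saying: "These are recommendations and final decisions should be made via clinical presentation and physician discretion". In the body, a pacemaker is one of several options, with an electrophysiologist consulted as needed, and C.4.7.2 leaves SAVR care to the surgeon's and hospital's usual practice. This also stands, and it is a main reason the point is minor.
- **The pacemaker endpoint may be wider than Class I or IIa.** O.2 separately defines permanent pacemaker implantation without reference to class. Labelling item 18 in C.6.10.1, which tests the new TAVI pacemaker rate against 30%, counts new implants and cites secondary objective 7. Item 18 may therefore count implants of any class. That is a fair reading of item 18. However, endpoint 7 carries the name of the class-limited O.2 term, and the class-free definition belongs to a different term.
- **The 35% has no clinical meaning.** It is a share of guideline entries, some of them rare or found only at electrophysiological study. That is correct, and the figure should be read only as a count.
- **The wording is the same in both arms, and the reason for each implant is recorded by 12-lead ECG beforehand.** Cases can therefore be checked against O.2 whatever the body text says, and the error creates no evident bias between arms. This also stands.

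**Conclusion.** The concern holds: the text is wrong as written, at minor severity. Both procedure sections name Class IIb where their cited source and the definition of the endpoint 7 term name Class IIa. Read literally, they omit 7 of the 20 criteria in Appendix R.13 and admit a class for which it lists none.

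The effect on the endpoint 7 rate cannot be calculated from the documents and is expected to be small. That expectation assumes that sites follow the cross-reference or their own judgement rather than the literal label, and that the heart-block bullets cover much of the most clear-cut omitted indication. The primary endpoint, its margin, the sample size, the analysis populations and the testing order are unaffected.

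**What to change.** In the Post-Procedure Pacing Guidelines of both C.4.7.1 and C.4.7.2, change Class IIb to Class IIa. The two sections will then agree with Appendix R.13 and with the O.2 definition.

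The cost is one letter in each of two places. No analysis, sample size or data collection changes.
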